In Phase I, we developed and pre-tested the social marketing campaign messages and delivery channels through focus groups and individual interviews of pregnant women, family members, and Elders. The focus group work assessed reasons for initiating or continuing tobacco use during pregnancy and the potential role of other community members in addressing tobacco use in pregnancy. Findings were used to develop campaign messages and media that were pre-tested through individual interviews and refined. Session content for the individually targeted intervention components was also developed to align with the campaign messages. Finally, the "Native Sisters" were hired and trained to deliver the intervention. In Phase II, we will conduct a cluster randomized trial with village as the unit of assignment with a control comparison condition to test the efficacy of the intervention on tobacco use during pregnancy and postpartum. This protocol modification updates Phase I results and activities as well as procedures for Phase II. The Aims for Phase II of the project are:

Aim 1. To evaluate the efficacy of the intervention compared with the control condition on the biochemically confirmed 7-day point prevalence tobacco use rate at week 36 gestation and at 6 months postpartum.

Hypothesis: Compared with the control condition, the intervention will be associated with significantly lower rates of tobacco use in late pregnancy (80% vs. 65%) and at 6 months postpartum (70% vs. 55%).

Aim 2. To examine the effect of the intervention on proposed social cognitive-theory based mediators of change including perceived social norms about tobacco use and self-efficacy for non-tobacco use.

Hypothesis: Intervention effects on tobacco use at week 36 gestation and at 6 months postpartum will be mediated by perceived self-efficacy and anti-tobacco norms.

Background (Include relevant experience, gaps in current knowledge, preliminary data, etc.):

Tobacco use during pregnancy and the postpartum period is a major public health problem in the U.S. The adverse effects of cigarette smoking during pregnancy and after delivery on maternal, fetal and infant health are well documented. A number of studies also report adverse health risks of prenatal smokeless tobacco (ST) use

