analyzed using either a NicAlert test strip at point of contact or by mailing the saliva sample to Mayo Clinic, Rochester, MN, laboratories for analysis. The biospecimens will be labeled using only the assigned study ID number with no other identifiers. Biochemical confirmation of self-reported tobacco abstinence during pregnancy is recommended due to high rates of nondisclosure, and cotinine is the recommended biomarker. As in other Alaska-based studies, the research staff will mail the woman a packet with detailed instructions for collecting and returning the sample by mail, a process shown to yield specimens consistent with in-person collection methods. There is precedence for obtaining saliva samples by mail to confirm tobacco abstinence in previous trials. Specimen samples will be shipped to Mayo Clinic for analysis. The lab results will be sent to the research assistant [name] at Mayo Clinic, Rochester for data entry. Once the specimen sample is processed and results posted, the sample will be destroyed immediately. We will assess NRT use at follow-up since use would elevate cotinine levels. Point-prevalence tobacco use will be defined as reported use of tobacco during the previous 7 days. For women who report no tobacco use, this will be confirmed with a salivary cotinine concentration of ≤ 20 ng/ml. Baseline tobacco users will be asked to report the number of quit attempts made and date of last attempt since enrollment. Also, baseline non-tobacco users will be asked to report any use and date of first use of tobacco since enrollment.

Table 2. Measures and Schedule of Assessments		# items	Pregnancy			Postpartum	
DATA COLLECTED (Reference #)			Baseline	12 weeks →	Week 36 Gestation	Week 8	Week 26
Socio-demographics (45)		10	X				
Self-reported tobacco use (3,149)		1	X	✗	X	X	X
Saliva specimen for analysis of cotinine		--	X		X		X
Tobacco users only: FTND/FTQ-ST (nicotine dependence) (147,148)		6	X				
Tobacco users only: Contemplation Ladder (readiness to quit) (121)		1	X	✗	X	X	X
Program evaluation		--		✗ →	← ✗	X	X
Theory-Based Variables (Mediators)							
Self-efficacy to quit or not use tobacco (150)		14	X	✗	X	X	X
Social norms about tobacco use (52)		6	X	✗	X	X	X
Social support for non-tobacco use (151)		1	X	✗	X	X	X
Other variables targeted							
Attitudes/perceived risks of Iqmik/tobacco use in pregnancy (66,152)		4	X	✗	X	X	X
SHS exposure: tobacco use of spouse/partner and household members, home restrictions on tobacco use (153-155)		4	X	✗	X	X	X

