We will follow procedures suggested by MacKinnon to assess mediation (**Aim 2**), fitting three GEE models to the data. We will first estimate the intervention effect separately for the dependent variable (with regression adjustment for covariates). That model provides an estimate of the total effect of the intervention, which MacKinnon labels C. Next we will estimate the intervention effect for each mediator (with regression adjustment for covariates); that model provides an estimate of the effect of the intervention on the mediator, which MacKinnon labels A. Finally we will estimate the mediated intervention effect for the dependent variable by adjusting for the mediator (and covariates); that model provides an estimate of the unmediated (i.e., direct) intervention effect, which MacKinnon labels C, and the intervention-adjusted effect of the mediator on the dependent variable, which MacKinnon labels B. Assuming an ICC of 0.01 and an effective sample size of 270 subjects after correction for the ICC, there will be 80% power to detect an effect size of at least 0.35 standard deviation units for paths A and B assuming a two-sided, alpha=0.05 test at 6-months postpartum.

Treatment condition differences on changes in other variables targeted (see Table 4) will be examined using GEE with a logit (binomial outcome) or identify (continuous outcome) links as appropriate.

We will summarize the cost of the program per pregnant woman enrolled (reached) along with cost per woman abstinent from tobacco at 6 months postpartum follow-up using descriptive statistics.

Endpoints

Primary:

Biochemically confirmed tobacco abstinence at 6-months post-partum.

Secondary:

Biochemically confirmed tobacco abstinence at end of pregnancy. Also, changes in proposed theory-based mediators of intervention efficacy.

Project Timeline

We have received approval from NIH to extend out the study timeline from 5 to 6 years total. We are currently beginning the 5th year of our 6-year NIH grant. Table 4 shows the timeline for the remaining Phase II

activities. We will request from NIH a 7th project year as a no-cost extension to complete analyses and dissemination if necessary and long as remaining funds permit.

Table 4

PROJECT TIMELINE, YEARS 3-7,
Dates: May 1, 2015 – April 30, 2020

Activity	Year 3 2015-2016				Year 4 2016-2017				Year 5 2017-2018				Year 6 2018-2019				Year 7 2019-2020 No Cost Extension					

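### On its natural reading the Aim 2 plan tests each mediator in its own outcome model, so a mediator with no effect of its own on tobacco use can appear to mediate if it correlates with one that has an effect

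*Combined protocol and SAP*

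**What the plan says.** The Aim 2 hypothesis (Aims for Phase II) names two mediators: "Intervention effects on tobacco use at week 36 gestation and at 6 months postpartum will be mediated by perceived self-efficacy and anti-tobacco norms". Table 2, the schedule of assessments, lists a third under the theory-based mediators, "Social support for non-tobacco use (151).

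The Aim 2 paragraph of the Phase II Data Analysis Plan describes "fitting three GEE models to the data": one for the total effect, one for path A, and one for path B with the direct effect. For path A it says "Next we will estimate the intervention effect for each mediator". For path B and the direct effect it says "Finally we will estimate the mediated intervention effect for the dependent variable by adjusting for the mediator (and covariates). The mediator is singular there, and path B is described as adjusted for the intervention, with no mention of another mediator.

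The covariates are not named, no correlation between mediators is given, and no rule for declaring mediation is stated (both paths significant, product of A and B, or a confidence interval). For power, the plan gives "Assuming an ICC of 0.01 and an effective sample size of 270 subjects after correction for the ICC" and claims "80% power to detect an effect size of at least 0.35 standard deviation units for paths A and B", two-sided at 0.05.

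**The concern.** The hypothesis attributes the effect to two constructs. The same counselling sessions are meant to shift norms and to build skills and support, and the constructs are measured in the same self-report interviews, so some correlation within women is plausible. With one mediator in the outcome model, its coefficient carries its own effect plus a share of the effect of any correlated mediator left out. If the intervention also moves it, path A is present too, and the pair of results looks like mediation.

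At stake is whether the trial can support a statement that norms and self-efficacy each carry part of the effect. There is no campaign-only arm, and the protocol plans to make intervention manuals and training available elsewhere in Alaska, so readers will look to Aim 2 for evidence on mechanism.

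**Working it through.** **Inputs from the documents:** 320 women in 16 villages (8 per arm), about 20 per village; ICC 0.01; effect size 0.35 SD; two-sided alpha 0.05; tobacco use at 6 months postpartum 70% against 55%, so abstinence 30% against 45%, pooled 37.5%; 14 degrees of freedom for the intervention test.

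**Assumed, because the documents do not give them:** the within-arm correlation of the mediators (0 to 0.7), the strength of the true mediator (log odds ratio 0.35 or 0.5 per SD), and the rule for declaring mediation (paths A and B both significant at 0.05).

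**Step 1: the plan's own figures.** Effective N = 320 / (1 + 19 × 0.01) = 320 / 1.19 = 268.9, stated as 270.
- Path A, 135 per arm: 0.35 × √(135/2) − 1.96 = 2.876 − 1.96 = 0.916, power 82%.
- Path B, comparing the mediator between 101.25 abstainers and 168.75 users (37.5% and 62.5% of 270): 0.35 × √(101.25 × 168.75 / 270) − 1.96 = 2.784 − 1.96 = 0.824, power 79.5%.

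The stated 80% is therefore reproduced by a calculation with one mediator at a time and no allowance for correlation between mediators.

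**Step 2: direction of the bias.** Let M1 affect tobacco use with coefficient B, and let M2 have no effect of its own but correlate ρ with M1 within arm. With M2 entered alone, its coefficient is roughly ρ × B. At B = 0.5 that gives 0.15, 0.25 and 0.35 for ρ = 0.3, 0.5 and 0.7; simulated absolute values were 0.138, 0.248 and 0.339. With both entered, the estimate for M2 was between 0.00 and 0.01 in absolute value.

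**Step 3: how often M2 is declared a mediator.** Simulation with 270 independent women, the intervention shifting M1 and M2 by 0.35 SD each, and abstinence calibrated to 30% against 45%. A log odds ratio of 0.35 per SD corresponds roughly to the plan's 0.35 SD.

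| Correlation | Single-mediator model, log OR 0.35 | Single-mediator model, log OR 0.5 | Joint model |
|---|---|---|---|
| 0 | 4% | 4% | about 4% |
| 0.3 | 10% | 17% | 3-4% |
| 0.5 | 21% | 37% | 3-4% |
| 0.7 | 39% | 62% | 3-4% |

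Repeat runs with other random seeds differ by 1 to 3 points.

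If the intervention does not move M2, path A fails and the single-mediator rate is 5% or fewer.

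**Step 4: check with clustering.** Exchangeable GEE, 16 villages of 20, ICC 0.01, small-sample standard errors and t with 14 df, log OR 0.35: single-mediator 9%, 16% and 33% at ρ = 0.3, 0.5 and 0.7; joint 3%, 3% and 4%. With 250 replicates per cell, the simulation standard error at 33% is √(0.33 × 0.67 / 250) = 3 points. The pattern is the same.

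**Step 5: what the joint model costs.** At log OR 0.35, the chance that the true mediator M1 is found on both paths falls from about 62% in the single-mediator model to 52% at ρ = 0.5 and 40% at ρ = 0.7.

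**The case against.** A reader might infer that an inert mediator will often appear to mediate in this trial. The documents do not support that. The correlation and the strength of the true mediator are assumptions, and at zero correlation the problem vanishes. Near the plan's own effect size and a correlation of 0.3 the rate is about 1 in 10. Higher figures, such as 24%, 42% and 72% at correlations of 0.3, 0.5 and 0.7, count significance of path B alone at log OR 0.5; mediation also needs path A. A mediator that does nothing at all, unmoved by the intervention, is rarely flagged. This part of the objection stands.

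It can also be said that the plan never states that mediators are entered one at a time, and that the unnamed covariates could include the other mediator. That is possible, but the singular wording points the other way, and a plan that relies on that reading has not specified it.

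Third, Aim 2 as worded concerns the effect of the intervention on the mediators. That is path A, which this bias does not touch. The hypothesis says that both constructs mediate, and the plan does not propose to rank or add the separate effects. This limits the point to claims of mediation by each construct.

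The strongest objection is that a joint model is not simply better. If norms act through self-efficacy, entering both blocks that route: in a check of that structure, detection of norms fell from 38% to 4% although norms did mediate. The documents do not settle the ordering. This stands, and it is why the joint model should be reported beside the single-mediator models and should not replace them.

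**Conclusion.** The concern holds in a limited form. On its natural reading, the plan cannot separate the two hypothesised mediators if they are correlated and the intervention moves both. Under those conditions, with 0.35 SD shifts and an effective sample of 270, a mediator with no effect of its own is declared a mediator in about 10-39% of trials at log OR 0.35 and 17-62% at 0.5, over correlations of 0.3 to 0.7; a joint model keeps this at 3-4%. The range rests on assumed correlations and path B sizes and on requiring both paths to be significant.

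It would go too far to infer that the planned Aim 2 analysis is invalid, or that its mediation results will usually be spurious. Path A is unaffected, the stated power reproduces for single-mediator models, and the primary comparison of tobacco use is untouched. The weakness lies in what a secondary, mechanistic aim can conclude, and it is cheap to repair.

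**What to change.** Add to the Aim 2 paragraph of the Phase II Data Analysis Plan, at week 36 gestation and at 6 months postpartum:

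- one GEE outcome model with self-efficacy and social norms (and social support) entered together with the intervention and named covariates;
- each specific A × B effect from that model with a confidence interval, and the observed correlations between mediators, reported beside the planned single-mediator results;
- a rule that separate mediation by each construct is claimed only where the joint model supports it;
- a statement that single-mediator estimates are kept and read as total mediated effects, since a joint model shows only the direct part of a mediator that acts through another.

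The cost is one extra model per time point on data already being collected. The plan should also say that its 80% power for path B does not carry over to the joint model, and give the loss shown above (about 62% to 52% or 40%) as a guide. If the mediators prove nearly uncorrelated, little precision is lost and the two sets of results should agree.

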In Phase II, we will conduct an evaluation of the intervention applying a group-randomized design with village as the unit of assignment. Sixteen villages were selected and randomly assigned to receive the intervention (8 villages) or control condition (8 villages) with ≥ 22 pregnant women recruited per village.

Subject population:

Sample size calculation. We estimate recruiting ≥ 22 pregnant women per village (N=352). Accounting for an estimated attrition rate of 10% due to miscarriage, abortion or fetal demise, we plan to achieve a final sample of at least 320 women eligible for follow-up. All pregnant women (tobacco users and non-users) will be eligible for enrollment.

Actual accrual. We met our targeted sample size of 352 women enrolled. Encouragingly, overall participation from control villages (n=164) was similar to overall participation from intervention villages (n=188). Although we estimated 22 or more women enrolled in each village, this was not feasible. Study villages were more or less interested in participating, with a range of 2 to 42 women enrolled in the 16 study villages.

Inclusion Criteria:

Participants consist of 352 Alaska Native pregnant adults age 18 and older. To be eligible for the study, Alaska Native pregnant women participants must:

- Be 18 years of age or older
- Provide written informed consent
- Currently 36 weeks or less gestation
- Access to a working telephone

Exclusion Criteria:

Individuals will be considered ineligible to participate in the study if they are:

- Not Alaska Native
- Under the age of 18
- Currently not pregnant or ≥ 37 weeks gestation
- No access to a working telephone
- Refuse to provide written informed consent

Will a Certificate of Confidentiality be obtained? If yes, provide an explanation.

No, a Certificate of Confidentiality will not be obtained.

Study Design

Methods: *Describe, in detail, the research activities that will be conducted under this protocol:*

Phase IA. Social Marketing Campaign Development

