up or who do not provide biochemical confirmation classified as using tobacco. The analysis will be supplemented with multiple imputation methods to classify lost to follow-up as tobacco users or non-users. GEE will also be used to examine condition differences on the point prevalence tobacco use rates at 12 weeks/week 36 gestation, and at 8 weeks postpartum. Because only 14 df are available for the test of the intervention we will employ a small sample correction to the standard GEE. For these analyses, the stratification factor (village size) will be adjusted for in the analysis. Based on the biochemically confirmed tobacco use status at baseline, in an exploratory fashion we will examine potential treatment effects separately among baseline non-tobacco users and tobacco users respectively using GEE. Within intervention villages only, exposure dose will be tested as a predictor of tobacco use at 36 weeks gestation and 6 months postpartum using GEE. A similar analysis will be performed using the intervention implementation index to examine potential dose response effects. Assuming an ICC of 0.01 and an effective sample size of 135 subjects in the intervention arm after correction for the ICC, there will be 80% power to detect an effect size of at least 0.5 standard deviation units when examining the association of intervention exposure (i.e., continuous measure) and abstinence rates. Potential village differences on intervention exposure or implementation will be summarized graphically and compared using GEE. The percentage of enrolled participants who complete 6- month follow-up postpartum (retention) will be compared between intervention and control villages using GEE.

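### The 80% power stated for mediation path A leaves out the 14 degrees of freedom that the plan gives for a test of the intervention, and it is a per-path figure, not the power for the Aim 2 hypothesis

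*Combined protocol and SAP*

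**What the plan says.** The Aim 2 hypothesis, at the start of the protocol, is that intervention effects on tobacco use at week 36 of gestation and at 6 months postpartum "will be mediated by perceived self-efficacy and anti-tobacco norms".

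The Phase II Data Analysis Plan fits three GEE models. Path A is the effect of the intervention on the mediator. Path B is the effect of the mediator on tobacco use, adjusted for the intervention. The power sentence begins "Assuming an ICC of 0.01 and an effective sample size of 270 subjects after correction for the ICC" and continues that "there will be 80% power to detect an effect size of at least 0.35 standard deviation units for paths A and B". The figure refers to the 6-month postpartum assessment and a two-sided 5% level.

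Earlier in the same section, in the tobacco-use analyses, the plan says: "Because only 14 df are available for the test of the intervention we will employ a small sample correction to the standard GEE".

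The plan gives no power for the mediated effect. It names no test of that effect beyond a reference to a published procedure.

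**The concern.** Two things do not fit together.

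- **Degrees of freedom.** Path A is a test of the intervention, and the intervention was assigned to 16 villages. The limit of 14 therefore applies to path A as much as to tobacco use. Correcting the sample size for the intra-class correlation widens the standard error, but it does not allow for estimating between-village variation from 16 units. The power sentence makes only the first correction.
- **Target of the power statement.** The hypothesis is mediation, which needs both paths to be non-zero. A power that holds for each path separately is higher than the power to find both.

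At stake is how Aim 2 is described. It is one of two Phase II aims, and changes in the mediators are a listed secondary endpoint. A reader who takes 80% as the power for Aim 2 would expect more from it than the design gives.

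**Working it through.** **Inputs from the documents**
- 16 villages, 8 per arm; average of 20 women per village, 320 in all; ICC 0.01 (Power Statement, Data Analysis Plan).
- Effective sample 270, so 135 per arm; 0.35 SD; two-sided alpha 0.05 (Data Analysis Plan).
- 14 degrees of freedom for the intervention test (Data Analysis Plan).
- Tobacco use at 6 months postpartum 70% against 55%, average 62.5% (Power Statement).

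**Reading of path B (assumption).** The 0.35 SD is taken as the difference in mean mediator score between users and non-users.

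**1. Effective sample.** 320 / (1 + 19 × 0.01) = 268.9, which agrees with 270.

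**2. The plan's own figure, path by path, large-sample test**
- Path A: noncentrality = 0.35 / √(2/135) = 2.876. Power = Φ(2.876 − 1.960) = 82.0% (81.7% by t on 268 degrees of freedom).
- Path B: 62.5% and 37.5% of 270 are 168.75 and 101.25. Noncentrality = 0.35 / √(1/168.75 + 1/101.25) = 2.784. Power = Φ(2.784 − 1.960) = 79.5%.

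So about 80% is reproduced for each path, but only with a large-sample reference.

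**3. Path A on 14 degrees of freedom.** The critical value rises from 1.960 to 2.145. Noncentral t with noncentrality 2.876 gives 76.2%. If the village-size stratum takes one more degree of freedom, 13 give 75.8%. Power of 80% on 14 needs a noncentrality of about 3.01, which is 3.01 × √(2/135) ≈ 0.367 SD.

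**4. Both paths significant.** The two tests are treated as independent, with a true effect of 0.35 SD on each path.

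| Reference distribution | Path A | Path B | Both |
|---|---|---|---|
| Large-sample for both | 82.0% | 79.5% | 65.2% |
| 14 df for A, large-sample for B | 76.2% | 79.5% | 60.6% |
| 14 df for both | 76.2% | 73.6% | 56.1% |

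A simulation of 16 villages of 20 women with ICC 0.01 (3,000 runs) gave 63% with 14 df on A and a large-sample test of B, and 58% with 14 df on both. Both results lie within the range of the table. For 80% joint power with 14 df on A, about 0.41 SD is needed on both paths.

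**5. Missing mediator scores (illustration; the 10% and 20% are assumed).** A woman lost to follow-up is classified as a tobacco user, but the plan states no corresponding rule for a mediator score.
- 10% missing: 288 women, 18 per village, effective sample 288 / (1 + 17 × 0.01) = 246.
- 20% missing: 256 women, 16 per village, effective sample 256 / (1 + 15 × 0.01) = 223.

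With 14 df on A and a large-sample test of B, joint power falls from 61% to about 55% and 49%.

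**The case against.** The strongest reply is that nothing in the sentence is miscalculated. It states its conditions, and on them each path reproduces. That stands. A reader might infer that the plan claims 80% power for mediation and that the true value is 60%. The documents do not support this. The sentence speaks of the paths and never of the mediated effect, and no fixed joint figure can be derived without choosing a test that the plan does not name.

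The conflict over degrees of freedom is also small: about 6 points against the large-sample figure and 4 against the stated 80%. Most of the distance to 61% comes from requiring both paths. The plan already recognises the 14 degrees of freedom and commits to a small-sample correction, though it says so with the tobacco-use analyses and does not repeat it for Aim 2.

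The joint figures can move up as well as down.
- Path B is largely a woman-level association. With no design effect (200 and 120 of 320 women), its power is 86%, and the joint figure with 14 df on A is 0.762 × 0.858 = 65%.
- The mediation models adjust for covariates that the plan does not list, and the mediators are measured at baseline. If the baseline score is included and correlates 0.3 with follow-up (assumption), noncentrality A becomes 2.876 / √(1 − 0.09) = 3.014 and path A is back at 80% on 14 df. At 0.5 (assumption) it is 87%, and the joint figure is 69% to 78%, depending on whether path B gains too.

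Finally, a reader might infer that a null mediation result will be taken as evidence that norms and self-efficacy do not matter. The plan sets no rule for interpreting a null result, so that is conjecture. None of these replies removes the omission of the 14 degrees of freedom from the path A figure, or the lack of any figure for the hypothesis itself.

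**Conclusion.** The point holds as an optimistic path A figure and an omission. It is not an arithmetic error. With the plan's own 14 degrees of freedom, path A has about 76% power at 0.35 SD, or 80% at about 0.37 SD, before any covariate gain. Path B is about 80% under a large-sample test. Neither figure is the power for the Aim 2 hypothesis. Under a rule that both paths must be significant, that power is roughly 56% to 65%, depending on where the 14 degrees of freedom are applied.

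The range assumes ICC 0.01, villages of 20 women, complete mediator data, near-independent tests, true effects of exactly 0.35 SD on both paths, and no gain from covariates. Missing scores would lower it, and adjustment for baseline mediators could raise it. It also leaves out the actual spread of 2 to 42 women per village.

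**What to change.** Restate the Aim 2 power sentence so that it does four things:
- gives about 76% power for path A at 0.35 SD on 14 degrees of freedom (or 80% at about 0.37 SD), and about 80% for path B;
- says that these are per-path figures;
- gives the power to find both paths significant as roughly 56% to 65%, with its assumptions: ICC 0.01, complete mediator data, no covariate gain;
- notes that missing mediator scores lower this and that adjustment for baseline mediators could raise it.

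The cost is a rewritten power statement and a slightly less favourable stated figure. Enrolment is complete, and no more women and no change of procedure are needed.
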